If topical rescue therapy as described above fails to sufficiently control AD symptoms, then oral systemic medications may be used as rescue (for example, corticosteroids, cyclosporine, and methotrexate). However, IP will be required to be permanently discontinued for the remainder of the 12-week study duration. If these medications are needed for other medical conditions (for example, asthma flare), they will still be treated as rescue medications.

Investigators should make every attempt to conduct efficacy and safety assessments immediately before administering any rescue treatment. An unscheduled visit can be used for this purpose if necessary.

7. Discontinuation of Study Intervention and Participant Discontinuation/Withdrawal

Participants discontinuing from the study intervention prematurely for any reason should complete AE and other follow-up procedures per Section 1.3 of this protocol.

Discontinuation of specific sites or of the study as a whole are handled as part of Appendix 1 (Section 10.1).

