7.1. Discontinuation of Study Intervention

In rare instances, it may be necessary for a participant to permanently discontinue (definitive discontinuation) study intervention. If study intervention is definitively discontinued, the participant will remain in the study for additional data collection, consistent with routine safety monitoring. See the SoA (Section 1.3) for data to be collected at the time of discontinuation of study intervention and follow-up and for any further evaluations that need to be completed.

The following infections lead to study intervention discontinuation: confirmed diagnosis of pneumocystis pneumonia, HIV, and active TB, including hepatitis B and C (as further described in Section 7.1.2).

A participant should be permanently discontinued from the study intervention

- if the participant becomes pregnant during the study
- for safety reasons, in the opinion of the investigator, or
- if the investigator determines that a systemic hypersensitivity reaction has occurred related to study intervention administration, the participant may be permanently discontinued from the study intervention, and the sponsor's designated medical monitor should be notified. If the investigator is uncertain about whether a systemic hypersensitivity reaction has occurred and whether discontinuation of study intervention is warranted, the investigator may consult the sponsor.

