7.1.5. Serious and Opportunistic Infections Discontinuation and Interruption Criteria

7.1.5.1. Discontinuation: The Following Infections Lead to Study Intervention Discontinuation

HBV or HCV: The participant tests positive for HBV DNA (see Section 8.2.10) or tests positive for HCV RNA (Section 8.2.11).

Note: The HBV DNA result is to be confirmed if initial test result is positive but below the level of quantification (Section 7.1.5.2). Prior to discontinuation of any immunomodulatory and/or immunosuppressive therapy, including study intervention, the participant is to be referred to, evaluated, and managed by a specialist physician with expertise in evaluation and management of viral hepatitis. The timing of discontinuation from study intervention relative to the initiation of any antiviral treatment for hepatitis is to be based on the recommendation of the consulting specialist physician, in conjunction with the investigator, and aligned with medical guidelines and standard of care.

Certain AEs:

- The participant develops HIV infection.
- The participant develops active TB or has untreated LTBI.

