7.1.5.2. Infection-Related Criteria for Temporary Withholding

Temporary withholding of study intervention is required if the participant meets any of the following infection-related criteria during the study:

- Serious or opportunistic infections, as defined in Section 5.2. Study intervention has to be withheld until resolution of all acute clinical signs and symptoms, and completion of all appropriate anti-infective treatment (exception for LTBI, noted below).
- A participant diagnosed with LTBI during the study has to be permanently discontinued from study intervention unless the participant is a candidate for LTBI treatment, and is treated for LTBI as follows:
 - o Study intervention is temporarily withheld for at least the first 4 weeks of LTBI treatment.
 - O After receiving at least 4 weeks of appropriate LTBI therapy (as per World Health Organization or US Centers for Disease Control and Prevention guidelines), if there is no evidence of hepatotoxicity (ALT/AST level must remain ≤2 times ULN) or other treatment intolerance, study intervention may be resumed.
 - The participant must complete appropriate LTBI therapy to remain eligible to receive study intervention.
- HBV DNA results that are reported as positive, or as detecting HBV DNA, but HBV DNA is below the level of quantification. In this situation, the sponsor's designated medical monitor should be contacted regarding the participant's status. HBV DNA testing is to be repeated as soon as it is feasible. If HBV DNA is confirmed as positive, the participant must be permanently discontinued from study intervention.

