7.2. Participant Discontinuation/Withdrawal from the Study

Discontinuation is expected to be uncommon.

A participant may withdraw from the study

- at any time at the participant's own request for any reason or without providing any reason
- at the request of the participant's designee (for example, parents or legal guardian)
- at the discretion of the investigator for safety, behavioral, compliance, or administrative reasons
- if enrolled in any other clinical study involving an IP or enrolled in any other type of medical research judged not to be scientifically or medically compatible with this study, and
- if the participant, for any reason, requires treatment with a therapeutic agent that is prohibited by the protocol and has been demonstrated to be effective for the treatment of the study indication. In this case, discontinuation from the study occurs prior to the introduction of the new agent.

At the time of discontinuing from the study, if possible, the participant will complete procedures for an early discontinuation visit as shown in the SoA (Section 1.3). If the participant has not already discontinued the study intervention, the participant will be permanently discontinued from the study intervention at the time of the decision to discontinue the study.

If the participant withdraws consent for disclosure of future information, the sponsor may retain and continue to use any data collected before such a withdrawal of consent. If a participant

withdraws from the study, the participant may request destruction of any samples taken and not tested, and the investigator must document this in the site study records.

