8.3.1. Timing and Mechanism for Collecting Events

This table describes the timing, deadlines, and mechanism for collecting events.

Event	Collection Start	Collection Stop	Timing for Reporting to Sponsor or Designee	Mechanism for Reporting	Back-up Method of Reporting
Adverse Event					
AE	Signing of ICF	Participation in study has ended	As soon as possible upon site awareness	AE CRF	NA
Serious Adverse	Event				
SAE and SAE updates – prior to start of study intervention and deemed reasonably possibly related to study procedures	Signing of ICF	Start of intervention	Within 24 hours of awareness	SAE CRF for mechanism of reporting and for back up SAE paper form	SAE CRF for mechanism of reporting and for back up SAE paper form
SAE and SAE updates – after start of study intervention	Start of intervention	Participation in study has ended	Within 24 hours of awareness	LSS SAE reporting process	NA
SAE* – after participant's study participation has ended and the investigator becomes aware	After participant's study participation has ended	NA	Promptly	SAE paper form	NA
Pregnancy					
Pregnancy in female participants and female partners of male participants	After the start of study intervention	Part A: 12 weeks after last dose. Part B: 14 weeks after last dose. Part C: 2 weeks after last dose.	Within 24 hours (see Section 8.3.2)	Pregnancy paper form	Pregnancy paper form
Product Compla		E 1 C . 1	W.1. 241 C	D 1 (C 11)	LATA
PC associated with an SAE or might have led to an SAE	Start of study intervention	End of study intervention	Within 24 hours of awareness	Product Complaint form	NA
PC not associated with an SAE	Start of study intervention	End of study intervention	Within 1 business day of awareness	Product Complaint form	NA
Updated PC information	_	_	As soon as possible upon site awareness	Originally completed Product	NA

				Complaint form	
				with all changes	
				signed and dated by	
				the investigator	
PC (if	Participation	NA	Promptly	Product Complaint	
investigator	in study has			form	
becomes aware)	ended				

Abbreviations: AE = adverse event; CRF = case report form; ICF = informed consent form; LSS = Lilly Safety System; NA = not applicable; PC = product complaint; SAE = serious adverse event.

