Beta D-glucand	FSH ⁱ
Cortisol (serum, cosyntropin stim, and urine)	Thyroid-stimulating hormone (including T3/T4 tests) Syphilis test (including RPR and TPPA as
	appropriate) ^g

Abbreviations: DNA = deoxyribonucleic acid; ED = early discontinuation; FSH = follicle-stimulating hormone; HIV = human immunodeficiency virus; Ig = immunoglobulin; NK cell = natural killer cell; RBC = red blood cell; RPR = Rapid Plasma Regain; TPPA = Treponema Pallidium Particle Agglutination.

Note: Results of these assays will be validated by the local laboratory at the time of testing. Additional tests may be performed or auto calculated by the laboratory as part of its standard panel that cannot be removed. Some of the above parameters are calculated from measured values. The omission of calculated values will not be considered as a protocol violation.

- a To be done centrally. If needed for safety, site may also perform locally.
- b Test only if dipstick result is abnormal.
- ^c Urine drug screen and ethanol breath testing may be repeated prior to admission to the clinical research unit and at other times indicated in the Schedule of Activities. Unscheduled testing is allowed.
- d Evaluation of beta-D-glucan may be performed at a local laboratory. Beta-D-glucan is required at screening for Part B only (to be performed centrally), and if an investigator believes it is warranted, at subsequent visits (may be performed centrally or locally), a beta-D-glucan test may be included in the work up panel at any time during the study. If the beta-D-glucan test is positive, pneumocystis pneumonia (PCP) needs to be ruled out. If PCP is ruled out and the investigator deems the patient fit to continue, the patient may continue in the study. If a patient has a confirmed diagnosis of PCP during the study, the patient must discontinue the study.
- e Not performed at screening.
- f Bedside glucose monitoring is performed using standard glucose monitors and capillary blood taken from fingerstick. Fasting should be approximately 2 hours, at a minimum.
- g Performed at screening only.
- h These tests may be waived if performed within 6 months prior to screening, and if test results are available for "review" for hepatitis B, C, and HIV.
- i To be performed on all female participants.

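### Appendix 2 footnote d takes a patient with confirmed pneumocystis pneumonia out of the study, while Section 7.1 stops the drug and keeps the patient in for follow-up

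*Protocol*

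**What the plan says.** Three pieces of current protocol text govern a patient whose PCP is confirmed on study.

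- **Appendix 2 (Section 10.2), footnote d**, attached to the beta-D-glucan test: "If a patient has a confirmed diagnosis of PCP during the study, the patient must discontinue the study". The sentence before it lets the patient stay in the study if PCP is ruled out and the investigator agrees.
- **Section 7.1**: "The following infections lead to study intervention discontinuation: confirmed diagnosis of pneumocystis pneumonia", followed by HIV, active TB and hepatitis B and C. The same section says that once study intervention is definitively discontinued, "the participant will remain in the study for additional data collection, consistent with routine safety monitoring".
- **Opening of Section 7**: "Participants discontinuing from the study intervention prematurely for any reason should complete AE and other follow-up procedures" according to the Schedule of Activities (SoA).

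Leaving the study is handled separately, in Section 7.2: "At the time of discontinuing from the study, if possible, the participant will complete procedures for an early discontinuation visit". Section 8.3.1 gives the stopping point for AE collection as "Participation in study has ended".

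**The concern.** The PCP sentence in Section 7.1 asks only that drug be stopped, and footnote d is compatible with that. The conflict is over what happens next: Section 7.1 keeps the patient under observation and footnote d removes the patient.

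If a site follows the footnote literally, scheduled follow-up gives way to a single visit, AE collection ends, and under Section 8.3 the investigator no longer has to look actively for new AEs or SAEs. The number and incidence of AEs, treatment-emergent AEs (TEAEs) and SAEs is the primary endpoint. SAP 10.6.1 counts any postdose AE as treatment-emergent, so events in the lost weeks belong to that endpoint. This would also happen in a patient with a confirmed infection, on a first-in-human drug for which Section 2.3 names infection as the primary predicted safety concern.

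**Working it through.** The plan gives no figure to reproduce. The check is a comparison of texts, followed by a count of SoA cells.

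**1. Do the instructions conflict?** For the same event, footnote d gives off study, and Section 7.1 gives off drug and on study. The protocol treats these as different states with different procedures (7.1 and 7.2). The withdrawal reasons in 7.2 do not name PCP, and footnote d does not present itself as an exception to Section 7.

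**2. Is PCP handled differently from the other listed infections?**
- Section 7.1 lists PCP, HIV, active TB, hepatitis B and hepatitis C: 5.
- Section 7.1.5.1, titled in part "The Following Infections Lead to Study Intervention Discontinuation", repeats the rule for hepatitis B, hepatitis C, HIV and active TB: 4.
- Left over: 5 − 4 = 1, which is PCP. It is also the only one of the five with text elsewhere that takes the patient out of the study.

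**3. What scheduled follow-up is at stake per case?** Section 4.1 puts the last Part B visit 14 weeks after the last dose. These are the marked cells in the follow-up columns of the two Part B schedules:

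| Assessment | Schedule 1.3.2.1 | Schedule 1.3.2.2 | ED column (each) |
|---|---|---|---|
| AE review | 4 (V801–V804) | 4 (V802–V805) | 1 |
| Hematology | 4 (V801–V804) | 3 (V803–V805) | 1 |
| Clinical chemistry | 4 (V801–V804) | 3 (V803–V805) | 1 |
| PK | 4 (V801–V804) | 5 (V801–V805) | 1 |

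Net loss = follow-up cells − assessments gained from an early discontinuation (ED) visit that takes place only under footnote d.

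- *No ED visit, or the same discontinuation assessment under both rules (gain 0):* AE reviews 4 or 4, hematology 4 or 3, chemistry 4 or 3, PK 4 or 5.
- *ED visit under footnote d only (gain 1):* AE reviews 4 − 1 = 3 or 4 − 1 = 3; hematology and chemistry each 4 − 1 = 3 or 3 − 1 = 2; PK 4 − 1 = 3 or 5 − 1 = 4.

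In each pair the first number is for schedule 1.3.2.1 and the second for 1.3.2.2. Treatment-period visits are left out, because the protocol does not say whether they continue once drug is stopped. The loss is smaller if PCP is confirmed after follow-up has begun.

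**The case against.** The best reply is that footnote d is loose wording. It is a note on working up a positive laboratory test, Section 7 is the governing section, and a site that turns to Section 7 finds an explicit answer. That may well be what the sponsor means. But the footnote's preceding sentence speaks of continuing in the study, so a literal contrast between in and out is a natural reading. The footnote is also the most specific instruction on PCP, which Section 7.1.5.1 omits.

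A second reply is that removal may be intended, since Section 7.2 allows withdrawal for safety and stops drug at the same time. That provision is discretionary, though. It does not create a mandatory exit for PCP or explain why Section 7.1 says the opposite.

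Several limits on the consequence stand:

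- Dosing stops under both rules.
- Section 8.3 still requires follow-up of the infection itself if it is serious, medically important, related, or the cause of stopping.
- A possibly related SAE that the investigator learns of later must still be reported.
- The protocol's own definition of a TEAE (Appendix 7) refers to a defined treatment period and is narrower than the SAP's, which softens the TEAE argument. The endpoint counts all AEs and SAEs as well, so it does not remove it.

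Section 8.3.2 sends a participant who has left the study on to the follow-up phase, but only for pregnancy.

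**Conclusion.** The inconsistency is real and lies in current operative text. Its importance is small. Cases should be rare, and dosing, sample size and planned analyses do not change. Per case, up to 14 weeks of Part B follow-up is affected: 3 to 4 AE reviews, 2 to 4 panels each of hematology and chemistry, and 3 to 5 PK time points, across both schedules and both ED-visit scenarios. These figures assume that a site takes footnote d literally and that PCP is confirmed before follow-up starts. What would be lost is routine safety visits and active seeking of new events; the PCP event itself would still be followed.

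**What to change.** Replace the last sentence of footnote d with wording to this effect: *On confirmed PCP, study intervention is stopped permanently and the patient stays in the study for safety follow-up under Section 7.1.* If the sponsor does intend removal from the study, Section 7.1 should instead state PCP as an exception and give the reason.

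Optionally, add a sentence to Section 7.1.5.2 saying that confirmed PCP falls under Section 7.1 and not under temporary withholding. For serious or opportunistic infections that section says "Study intervention has to be withheld until resolution of all acute clinical signs and symptoms", which could suggest that drug may be restarted. The main correction does not depend on this addition.

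The cost is one footnote sentence and, if wanted, one more in 7.1.5.2. Visits, sample size and analysis stay as they are.

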4.1. Overall Design

Study KMAA is a first-in-human trial designed to characterize the safety and tolerability of LY3872386 as well as the PK of LY3872386, total antibody, and LY3558533 (free payload) in healthy participants and in patients with AD. Additionally, this study will assess the safety, PK, tolerability, and PD of various dose levels of prednisone in healthy participants. The study will enroll participants of any ethnicity. The inclusion of healthy Japanese and Chinese participants in Part A, the LY3872386 SAD portion of this study, will facilitate the inclusion of Japanese and Chinese participants in subsequent clinical trials. The study will be conducted in 3 parts as follows:

- Part A (SAD of LY3872386) will characterize the safety, tolerability, PK, and PD after single IV and SC dose administration of LY3872386 in healthy participants.
- Part B (MAD of LY3872386) will characterize the safety, tolerability, PK, and PD after multiple SC and/or IV dose administrations of LY3872386 in patients with AD.
- Part C CCI will assess the safety, tolerability, PK, and PD after repeat PO administration of prednisone in healthy participants.

Section 1.2 illustrates the study schema and demonstrates the relationship among Parts A, B, and C. Section 1.2 also provides details on dosing and the inclusion of healthy Chinese and Japanese participants. Part A will begin first and will inform and thereby trigger the initiation of Parts B and C.

Screening Period

Screening may occur up to 35 days prior to Day 1 of the study. After obtaining informed consent, participants will be screened for eligibility as detailed in Section 5. Screening procedures will be performed as outlined in the SoA (Section 1.3).

[figure not shown]
Participants who are not enrolled within 35 days of screening may be subjected to an additional medical assessment and/or clinical measurements to confirm their eligibility. The assessments will be repeated at the discretion of the investigator.

Treatment Period and Visit Frequency

Part A: SAD of LY3872386 in Healthy Participants

Part A will be a SAD study of LY3872386 in healthy participants and will be comprised of 8 cohorts. SAD Cohorts 1 to 5 will consist of CCI healthy participants each who will be randomly assigned to receive LY3872386:placebo in a commanner. SAD Cohorts 6 to 8 will consist of CCI participants who will be randomly assigned to receive LY3872386:placebo in a commanner. See Table KMAA.1 for further details.

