- 22. show evidence of active or latent TB, as documented through medical history and examination, chest x-rays (posterior to anterior, read by a radiologist, pulmonologist, or designee; a lateral chest x-ray may be performed if clinically or radiologically indicated), and TB testing, either a positive tuberculin skin test (TST; defined as a skin induration >5 mm at 48 to 72 hours, regardless of Bacillus Calmette-Guérin or other vaccination history) or a positive QuantiFERON®-TB Gold test. If the QuantiFERON-TB Gold test result is indeterminate, it may be repeated only once, and if the repeat test is indeterminate, the participant will be deemed ineligible. The choice to perform a TST or a QuantiFERON-TB Gold test will be made by the investigator according to local standard of care. Please note that if a chest x-ray has been performed in the past 6

months, found to be normal and the report is available, a further chest x-ray is not required, provided there has been no known TB exposure since the x-ray was performed.

Note: Results of a chest CT scan or other imaging study similar to a chest x-ray may be substituted in place of the chest x-ray as described above, in consultation with the sponsor's medical monitor.

- 23. have 1 of the following viral infections:
 - a. a current infection with HBV (that is, positive for HBsAg and/or polymerase chain reaction positive for HBV DNA; Section 8.2.10).
 - b. a current infection with HCV (that is, positive for HCV RNA; Section 8.2.11).
 - c. HIV infection.
- 24. had any surgical procedure (except for minor surgery requiring local or no anesthesia and without any complications or sequelae) within 12 weeks prior to screening or any planned surgical procedure scheduled to occur during the study.
- 25. have a history or presence of multiple or severe allergies or an anaphylactic reaction to prescription or nonprescription drugs.
- 26. have a history or presence of allergy or reactions to ADC, mAbs, systemic GCs or have clinically significant multiple or severe drug allergies, intolerance to TCSs (for healthy participants only), or a history of severe posttreatment hypersensitivity reactions (including, but not limited to, erythema multiforme major, linear immunoglobulin A dermatosis, toxic epidermal necrolysis, or exfoliative dermatitis).

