8.2.10. Hepatitis B Testing and Monitoring

Testing

Testing for HBV infection includes HBsAg and anti-HBc.

- If HBsAg is positive, the participant is excluded.
- If HBsAg is negative and anti-HBc is negative, the participant is not excluded.

b In participants with Gilbert's syndrome, the threshold for TBL may be higher.

• If HBsAg is negative and anti-HBc is positive, further testing for HBV DNA is required.

- o If the screening HBV DNA is positive, the participant is excluded.
- o If the screening HBV DNA is negative, the participant is not excluded.

Monitoring

If the screening HBV DNA is negative, and proof of HBV vaccination cannot be provided, repeat testing for HBV DNA is required at least every 3 months during the study.

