10.2. Appendix 2: Clinical Laboratory Tests

The tests detailed in the table below will be performed by the central laboratory except for the following which will be performed at the local laboratory:

- Safety testing for immediate participant assessment
- Screening assessments in Part A and Part C.

In circumstances where the sponsor approves local laboratory testing in lieu of central laboratory testing (in the table below), the local laboratory must be qualified in accordance with applicable local regulations.

Protocol-specific requirements for inclusion or exclusion of participants are detailed in Section 5 of the protocol.

Additional tests may be performed at any time during the study as determined necessary by the investigator to address any immediate patient safety concerns.

Investigators must document their review of the laboratory safety results.

Laboratory results that could unblind the study will not be reported to investigative sites or other blinded personnel.

Safety Laboratory Tests

TH	GILL LGI
Hematologya	Clinical Chemistrya
Hematocrit	Sodium
Hemoglobin	Potassium
Erythrocyte count (RBC)	Bicarbonate
Mean cell volume	Chloride
Mean cell hemoglobin	Calcium (total)
Mean cell hemoglobin concentration	Phosphorus/Phosphate
Leukocytes (white blood cells [WBCs])	Glucose (fasting)
Platelets	Blood urea nitrogen (BUN)
Differential WBC (absolute counts) of	Creatinine
Neutrophils	Total protein
Lymphocytes	Albumin
Monocytes	Total bilirubin
Eosinophils	Alkaline phosphatase (ALP)
Basophils	Aspartate aminotransferase (AST)
B Cells	Alanine aminotransferase (ALT)
T Cells	Gamma-glutamyl transferase (GGT)
NK cells	Insuline
Hemoglobin A1c	Bedside Glucose Monitoring (fasting)f
Urinalysis ^a	Serum Immunoglobulinsa
Specific gravity	IgA
рН	IgM
Protein	IgE
Glucose	IgG
Ketones	IgD
Bilirubin	192
Urobilinogen	Fasting Lipid Panel ^a
Leukocytes	Total cholesterol
Blood	Triglycerides
Nitrite	Low-density lipoprotein (LDL)
	High-density lipoprotein (HDL)
Microscopic examination of sedimentb	
	LDL/HDL ratio
H. D. C.	T W D C W all
Urine Drug Screen ^c	Hepatitis B surface antigeng,h
Amphetamine	Hepatitis B core antibodyg,h
Barbiturates	Hepatitis B surface antibodyg,h
Benzodiazepines	Hepatitis B DNAh
Cocaine	Hepatitis C antibodyg,h
Cannabis	riepatitis C antibody
Methylenedioxymethamphetamine (MDMA)	
Opiates	
Oxycodone	
Phencyclidine	
Tricyclic antidepressants	
Cotinine (nicotine)	
	gh
Ethanol breath testing ^c	$HIV^{g,h}$
QuantiFERON®-TB Gold test or TST	Pregnancy test ⁱ

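### Footnote h in Appendix 2 lets an HBV DNA result up to 6 months older than screening stand in for the test that decides entry of anti-HBc-positive participants, and the protocol does not say whether it or Section 8.2.10 prevails

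*Protocol*

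**What the plan says.** The laboratory table in Protocol Section 10.2 lists "Hepatitis B DNAh"; the final letter is the footnote marker. Footnote h reads: "These tests may be waived if performed within 6 months prior to screening, and if test results are available", and it names hepatitis B, hepatitis C and HIV. The HBV serologies carry the same marker.

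Section 8.2.10 governs hepatitis B eligibility. On the reflex test it says: "If HBsAg is negative and anti-HBc is positive, further testing for HBV DNA is required". A positive screening result excludes; for a negative one, "If the screening HBV DNA is negative, the participant is not excluded". Criterion 23a in Section 5.2 excludes "a current infection with HBV (that is, positive for HBsAg and/or polymerase chain reaction positive for HBV DNA" and cites Section 8.2.10, not Appendix 2.

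After entry, Section 8.2.10 sets a repeat rule for those admitted on a negative result. It applies where "proof of HBV vaccination cannot be provided, repeat testing for HBV DNA is required at least every 3 months during the study". The note to criterion 49 sets a monthly interval for Japanese patients in Part B. Neither text says when the interval starts.

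On timing, Section 4.1 states: "Screening may occur up to 35 days prior to Day 1 of the study". It adds: "Participants who are not enrolled within 35 days of screening may be subjected to an additional medical assessment", with the repeat left to the investigator's discretion, so 35 days is the plan and not a hard limit.

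**The concern.** For someone who is HBsAg-negative and anti-HBc-positive, HBV DNA is the only test left that decides entry. Section 8.2.10 speaks of a screening result; footnote h allows an older one. A site following the appendix can admit this participant on a sample drawn months before screening and believe that it complied.

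Section 2.3 acknowledges that LY3872386 may reactivate latent infections and gives that as the reason to screen for hepatitis B. The drug is a first-in-human conjugate with a glucocorticoid payload, and healthy participants have no expected benefit. At stake is a first dose given to someone with viraemia that arose after the old sample.

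The gap between draw and dose matters most in Part B. Criterion 12 admits patients who failed systemic immunosuppressants during the 6 months before screening, the same period the waiver covers. Such drugs may be taken after the waived draw and up to the washout (4 weeks under criterion 46b, or 30 days or 5 half-lives under criterion 18 if longer). Footnote h sets no condition on what happened in between. Criterion 22, by contrast, accepts a chest x-ray up to 6 months old only if there has been no known TB exposure since.

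**Working it through.** The plan states no figure for the age of the DNA result at first dose, so this is a comparison of texts plus date arithmetic.

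**Which text governs**

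| Source | Content | Favours |
|---|---|---|
| 10.2 table and footnote h | HBV DNA may be waived on a prior result | waiver |
| 8.2.10 | DNA required for this subgroup; entry rests on the screening result | new test |
| 5.2, criterion 23a | current infection; cites 8.2.10 | new test |
| 10.2, text above the table | points to Section 5 for eligibility | leans to new test, does not cancel the waiver |
| 8, general rules | screening evaluations to be completed and reviewed | does not mention the waiver |

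The two rules could be reconciled by counting the earlier result as the screening result. The protocol does not say so, and that reading still accepts the old sample.

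**Inputs.** Waiver period 6 months, about 183 days (10.2, footnote h). Screening window 35 days (4.1). General repeat interval 3 months, about 91 days (8.2.10). Part A follow-up 12 weeks, or 84 days, after the dose (4.1).

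**Age of the deciding result at Day 1**
- With the waiver: 183 + 35 = 218 days, about 7 months.
- With a test drawn in the screening period: at most 35 days as planned.
- Against the 3-month repeat interval: 218 / 91 = 2.4 times as long.

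**Immunosuppressant exposure after the draw (Part B).** With a 4-week washout, up to 218 − 28 = 190 days of possible use lie between draw and washout. With 30 days, 218 − 30 = 188 days.

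**Does the 3-month repeat close the gap?** It applies only without proof of vaccination. Its start is not stated, so all three are shown:

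| Clock starts at | First repeat due | Maximum age of latest DNA at first dose |
|---|---|---|
| Waived draw | By Day 1 if the draw is more than 91 days old (the oldest is overdue by 218 − 91 = 127 days) | about 91 days |
| Screening, 35 days before Day 1 | 91 − 35 = 56 days after Day 1, i.e. Day 57 | about 218 days |
| Day 1 | Day 92 | about 218 days |

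With proof of vaccination no repeat is required, and about 218 days stands under every start.

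Part A ends about Day 85 (84 days after Day 1). Counted from Day 1, no repeat falls due in Part A; counted from screening, at most one does, after the single dose has been given.

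**The case against.** The strongest reply is that Section 8.2.10 already prevails. Section 10.2 sends eligibility to Section 5, criterion 23a cites 8.2.10, and 8.2.10 is the specific rule, whereas footnote h is general and permissive. The cross-references do lean that way. They do not withdraw a waiver printed on this very test, however, and if 8.2.10 governs, the marker is an error that invites sites to skip a required test. Either reading leads to the same correction.

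Most comment cells in the Schedule of Activities are blacked out, so a clarification there cannot be excluded. The one surviving comment on the serologies row (Section 1.3.3.2) only points back to Section 10.2.

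Footnote h also lets the serologies be 6 months old at screening, and these decide who gets a DNA test at all. That is true, and the proposed change leaves it so. The point is kept to DNA because there the waiver meets wording that requires a test and rests entry on the screening result.

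Other safeguards exist: ALT and AST at screening, investigator discretion to exclude or to add tests, and discontinuation with specialist referral if HBV DNA turns positive on study. They reduce the consequences. But the hepatitis work-up in Section 8.2.8 starts only after liver tests rise, and stopping treatment cannot undo the single dose in Part A. None ensures a current DNA result before dosing.

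Finally, the affected group is probably small. Nothing in the documents suggests that healthy volunteers would have a prior DNA result on file. This stands, and it limits the weight of the point.

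**Conclusion.** The concern holds. Footnote h permits an entry decision on an HBV DNA result up to about 218 days old at first dose, against 35 days as planned if the sample is drawn during screening. The visible text does not resolve the conflict with Section 8.2.10.

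This rests on 6 months taken as 183 days, 3 months as 91 days and full use of the 35-day window, which can itself be exceeded. If the repeat clock runs from the waived draw and there is no proof of vaccination, the maximum is about 91 days instead of 218. Harm needs an HBsAg-negative, anti-HBc-positive participant, an available prior DNA result, a site that chooses the optional waiver, and viraemia that arose since. The documents give no number for any of these, so the size is stated as the age of a test and not as a risk. The change should be made as a cheap safety improvement; it does not affect the trial's analyses.

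**What to change.** Remove footnote h from the hepatitis B DNA entry in Section 10.2, so that anyone who needs a DNA result for eligibility has it drawn during the screening period. Keep the 6-month waiver for the serologies.

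The planned maximum age of the result at Day 1 falls from about 218 to 35 days, still subject to the discretion in Section 4.1 when enrolment runs past the window. The cost is one footnote marker in a protocol amendment, with the ethics approval that Section 10.1.1 requires, plus one tube and the wait for its result in the few participants concerned. The assay is already planned.
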